### **Day 7 (inpatient)**

Prior to dosing of tepotinib on Day 7 the following will be done:

- Vital signs
- 12-lead ECG
- Blood and urine samples for safety laboratory assessments
- Pre-dose PK blood sample for determination of tepotinib and metabolites parameters

After completion of the pre-dose assessments a standardized breakfast will be served and tepotinib will be administered 30 min after start of breakfast. At 4 h after administration the subjects will consume a standardized lunch. Six hours after drug administration, vital signs will be measured and an ECG recorded.

After dosing blood samples for determination of tepotinib and its metabolites will be taken (please refer to [Table 2](#)). Subjects will be asked regularly about their well-being and any medication taken.

### **Day 8 to 11 (inpatient)**

Prior to dosing on Day 8 the following will be done:

- Vital signs

- 12-lead ECG
- Blood and urine samples for safety laboratory assessments
- Pre-dose PK blood sample will be taken for determination of total dabigatran, tepotinib and its metabolites and coagulation parameters

After completion of the pre-dose assessments a standardized breakfast will be served and dabigatran etexilate and tepotinib will be administered 30 min after start of breakfast. At 4 h after administration of study drugs the subjects will consume a standardized lunch.

After dosing safety assessments (vital signs, 12-lead ECGs) will be performed regularly and blood samples for determination of total dabigatran and coagulation parameters will be taken (please refer to [Table 2](#)). Prior to discharge on Day 11 blood and urine samples will be taken in addition for safety laboratory assessments. Subjects will be asked regularly about their well-being and any medication taken.

Details about the measurements are provided in Sections [7.4](#) and [7.5.1](#).

**Dietary Regimen:**

The subjects will be fasting at least 10 h before a standardized breakfast will be provided. Thereafter administration of dabigatran etexilate and/or tepotinib will occur (see Section [6.2](#)). Four (4) hours after administration of dabigatran etexilate, a standardized lunch will be served. An afternoon snack will be provided 8 h and dinner 10 h post-dose.

On Day 1 of Period 1 and on Day 1 to 8 of Period 2, tepotinib and/or dabigatran etexilate will be administered 30 min after a defined standardized breakfast. All other meals during the inpatient period will be served as customary at the trial center.

During hospitalization subjects are not allowed to eat other than the provided meals.

Subjects should drink about 2 L fluids per day during the hospitalization phase (as provided by the site) and will be reminded regularly (for restrictions of fluids see below).

**Restrictions:**

**Foods, sweets and beverages:**

Intake of herbs/fruits that can have an influence on PK (eg St. John's Wort, Seville oranges, grapefruits, cranberry or the juice of these fruits) are not allowed from 14 days before Day -1 of Period 1 until final examination. Methylxanthines (eg coffee, tea, cola, and cocoa) and alcohol containing food or beverages are not allowed from 48 h prior to the intended start of trial drug administration until the last PK blood sample. Poppy seeds (eg poppy seed rolls, poppy seed cake, yoghurt containing poppy seed etc.) will not be allowed from 72 h prior to dosing until completion of final examinations.

**Drinking of fluids:**

Drinking of fluids is not allowed 1 h after administration of dabigatran etexilate or tepotinib.

**Smoking:**

Only non-smokers or smokers who stopped smoking at least 6 months before the time of the Screening Visit will be included in the trial. Moreover, smoking is not allowed from Screening Visit until completion of End of Trial Visit.

**Exercise Regimen:**

Subjects will be advised to avoid heavy physical exertion 72 h prior to first drug administration until completion of all post trial examinations.

**7.1.3                   End of Trial Visit**

The End of Trial examination should verify that all values tested in the Screening have remained within a clinically acceptable range. The assessments will be performed on  $7 \pm 1$  day after last drug administration in Period 2 or upon premature termination. Unacceptable values and AEs will be followed up until they return to the reference ranges/resolved or there is an adequate explanation which is not related to the trial.

The End of Trial examination will consist of the following:

- Physical examination
- Vital signs
- 12-lead ECG
- Blood and urine samples for safety laboratory assessments and coagulation parameters (including a serum pregnancy test)
- Concomitant medication
- Assessment of AEs

No medical treatment is planned after the end of the trial.

The end of the trial is defined as the last contact (related to this trial) of the last subject undergoing the trial.

**7.2                   Demographic and Other Baseline Characteristics**

At Screening, the following demographic data will be collected: age (year of birth), height, weight, BMI, gender, race and ethnicity.

Furthermore, the following will be documented:

- Clinically relevant findings in the medical history are recorded
- Prior medication within 14 days (any prescribed medicine or over-the-counter drug or dietary supplement including herbal remedies, vitamins, and minerals)

- Smoking status, alcohol intake
- Female status (contraception, postmenopausal, sterilization).

### **7.3 Efficacy Assessments**

Not applicable.

### **7.4 Assessment of Safety**

The safety profile of the IMPs will be assessed through the recording, reporting and analysis of baseline medical conditions, AEs, physical examination findings including vital signs, ECGs and laboratory tests.

Comprehensive assessment of any apparent toxicity experienced by each subject will be performed from the time of giving informed consent and throughout the trial. The Investigator will report any AEs, whether observed by the Investigator or reported by the subject (see Section 7.4.1.2). The reporting period for AEs is described in Section 7.4.1.3.

#### **7.4.1 Adverse Events**

##### **7.4.1.1 Adverse Event Definitions**

###### **Adverse Event**

An AE is any untoward medical occurrence in a subject or clinical investigation subject administered a pharmaceutical product, regardless of causal relationship with this treatment. An AE can therefore be any unfavorable and unintended sign (including an abnormal laboratory finding), symptom, or disease temporally associated with the use of a medicinal product, whether or not considered related to the medicinal product.

For surgical or diagnostic procedures, the condition/illness leading to such a procedure is considered as the AE rather than the procedure itself.

The Investigator is required to grade the severity or toxicity of each AE. Investigators will reference the National Cancer Institute - Common Terminology Criteria for AEs (NCI-CTCAE), Version 5.0 (publication date: 27 Nov 2017), a descriptive terminology that can be used for AE reporting. A general grading (severity/intensity; hereafter referred to as severity) scale is provided at the beginning of the above referenced document, and specific event grades are also provided. If the severity for an AE is not specifically graded by NCI-CTCAE, the Investigator is to use the general NCI-CTCAE definitions of Grade 1 through Grade 5, using his or her best medical judgment.

The 5 general grades are:

- Grade 1 or Mild
- Grade 2 or Moderate
- Grade 3 or Severe
- Grade 4 or Life-threatening

### Grade 5 or Death

Any clinical AE with severity of Grade 4 or 5 must also be reported as an SAE. However, a laboratory abnormality of Grade 4, such as hemoglobin decreased or neutrophils count decreased, is considered serious only if the condition meets one of the serious criteria specified below.

If death occurs, the primary cause of death or event leading to death should be recorded and reported as an SAE. “Fatal” will be recorded as the outcome of this specific event and death will not be recorded as separate event. Only, if no cause of death can be reported (eg, sudden death, unexplained death), the death per se might then be reported as an SAE.

Investigators must also systematically assess the causal relationship of AEs to IMPs (including any other non-IMPs, radiation therapy, etc.) using the following definitions. Decisive factors for the assessment of causal relationship of an AE to the IMPs include, but may not be limited to, temporal relationship between the AE and the IMPs known side effects of IMPs, medical history, concomitant medication, course of the underlying disease, trial procedures.

**Unrelated:** Not reasonably related to the IMPs. AE could not medically (pharmacologically/clinically) be attributed to the IMP/trial treatment under trial in this clinical trial protocol. A reasonable alternative explanation must be available

**Related:** Reasonably related to the IMPs. AE could medically (pharmacologically/clinically) be attributed to the IMPs under trial in this clinical trial protocol.

### Abnormal Laboratory Findings and Other Abnormal Investigational Findings

Abnormal laboratory findings and other abnormal investigational findings (for example, on an ECG trace) should not be reported as AEs unless they are associated with clinical signs and symptoms, lead to treatment discontinuation or are considered otherwise medically important by the Investigator. If a laboratory abnormality fulfills these criteria, the identified medical condition (for example, anemia, increased ALT) must be reported as the AE rather than the abnormal value itself.

### Serious Adverse Events

An SAE is any untoward medical occurrence that at any dose:

- Results in death
- Is life-threatening. (Note: The term “life-threatening” refers to an event in which the subject is at risk of death at the time of the event, not an event that hypothetically might have caused death if it was more severe.)
- Requires inpatient hospitalization or prolongs an existing hospitalization
- Results in persistent or significant disability or incapacity
- Is a congenital anomaly or birth defect

- Is otherwise considered to be medically important. (Note: Important medical events that may not result in death, be life-threatening, or require hospitalization may be considered as SAEs when, based upon appropriate medical judgment, they may jeopardize the subject or may require medical or surgical intervention to prevent one of the outcomes listed above. Examples of such events include allergic bronchospasm requiring intensive treatment in an emergency room or at home, blood dyscrasias or convulsions that do not result in inpatient hospitalization, or the development of drug dependency or drug abuse.)

For the purposes of reporting, any suspected transmission of an infectious agent via an IMP is also considered an SAE, as described in Section [7.4.1.4](#).

#### **Events that Do Not Meet the Definition of an SAE**

Elective hospitalizations to administer, or to simplify trial treatment or trial procedures (for example, an overnight stay to facilitate chemotherapy and related intravenous fluid administration) are not considered SAEs. However, all events leading to unplanned hospitalizations or unplanned prolongation of an elective hospitalization (for example, undesirable effects of any administered treatment) must be documented and reported as SAEs.

#### **7.4.1.2 Methods of Recording and Assessing Adverse Events**

At each trial visit, the subject will be queried on changes in his or her condition. During the reporting period, any unfavorable changes in the subject's condition will be recorded as AEs, whether reported by the subject or observed by the Investigator.

Complete, accurate and consistent data on all AEs experienced for the duration of the reporting period (defined below) will be reported on an ongoing basis in the appropriate section of the eCRF. All SAEs must be additionally documented and reported using the appropriate Report Form as described in Section [7.4.1.4](#).

It is important that each AE report include a description of the event, its duration (onset and resolution dates (and times) when it is important to assess the time of AE onset relative to the recorded treatment administration time), its severity, its causal relationship with the trial treatment, any other potential causal factors, any treatment given or other action taken, including dose modification or discontinuation of the IMP, and its outcome. In addition, serious cases should be identified and the appropriate seriousness criteria documented.

Specific guidance can be found in the eCRF Completion and Monitoring Conventions.

#### **7.4.1.3 Definition of the Adverse Event Reporting Period**

The AE reporting period for safety surveillance begins when the subject is initially included in the trial (date of first signature of informed consent) and continues until the End of Trial Visit.

Any SAE assessed as related to the IMPs must be reported whenever it occurs, irrespective of the time elapsed since the last administration of IMPs.

#### **7.4.1.4      Procedure for Reporting Serious Adverse Events, Adverse Events of Special Interest and Dose Limiting Toxicities**

##### **Serious Adverse Events**

In the event of any new SAE occurring during the reporting period, the Investigator must immediately (within a maximum of **24 hours** after becoming aware of the event) inform the Sponsor or its designee in writing. All written reports should be transmitted using the SAE Report Form, which must be completed by the Investigator following specific completion instructions.

In exceptional circumstances, an SAE (or follow-up information) may be reported by telephone; in these cases, a written report must be sent immediately thereafter by fax or e-mail. Names, addresses, and telephone and fax numbers for SAE reporting will be included in the trial-specific SAE Report Form.

Relevant pages from the eCRF may be provided in parallel (for example, medical history, concomitant drugs). Additional documents may be provided by the Investigator, if available (for example, laboratory results, hospital report, and autopsy report). In all cases, the information provided on the SAE Report Form must be consistent with the data about the event recorded in the eCRF.

The Investigator must respond to any request for follow-up information (for example, additional information, outcome, final evaluation, other records where needed) or to any question the Sponsor/designee may have on the AE within the same timelines as those noted above for initial reports. This is necessary to ensure prompt assessment of the event by the Sponsor or designee and (as applicable) to allow the Sponsor to meet strict regulatory timelines associated with expedited safety reporting obligations.

Requests for follow-up will usually be made via the responsible Monitor, although in exceptional circumstances the Global Drug Safety department may contact the Investigator directly to obtain further information or to discuss the event.

##### **Adverse Events of Special Interest**

Healthy subjects might experience asymptomatic elevations in serum lipase and amylase. Any elevation in serum lipase and amylase of Grade  $\geq 3$  will lead to the recording of an adverse event of special interest (AESI). The severity of these AEs should be defined based on clinical judgment of the Investigator and defined according to NCI-CTCAE Severity Scale.

#### **7.4.1.5      Safety Reporting to Health Authorities, Independent Ethics Committees/ Institutional Review Boards and Investigators**

The Sponsor will send appropriate safety notifications to Health Authorities in accordance with applicable laws and regulations.

The Investigator must comply with any applicable site-specific requirements related to the reporting of SAEs (particularly deaths) involving trial subjects to the IEC that approved the trial.

In accordance with ICH GCP, the Sponsor/designee will inform the Investigator of “findings that could adversely affect the safety of subjects, impact the conduct of the trial or alter the IEC’s approval/favorable opinion to continue the trial.” In line with respective regulations, the Sponsor/designee will inform the Investigator of AEs that are both serious and unexpected and are considered to be related to the administered product (“suspected unexpected serious adverse reactions” or SUSARs). The Investigator should place copies of Safety Reports in the Investigator Site File. National regulations regarding Safety Report notifications to Investigators will be considered.

When specifically required by regulations and guidelines, the Sponsor/designee will provide appropriate Safety Reports directly to the concerned lead IEC and will maintain records of these notifications. When direct reporting is not clearly defined by national or site-specific regulations, the Investigator will be responsible for promptly notifying the concerned IEC of any Safety Reports provided by the Sponsor/designee and of filing copies of all related correspondence in the Investigator Site File.

For trials covered by the European Directive 2001/20/EC, the Sponsor’s responsibilities regarding the reporting of SAEs/SUSARs/Safety Issues will be carried out in accordance with that Directive and with the related Detailed Guidance documents.

#### **7.4.1.6 Monitoring of Subjects with Adverse Events**

AEs are recorded and assessed continuously throughout the trial (see Section 7.4.1.3) and are assessed for final outcome at the End of Trial Visit. All SAEs ongoing at the End of Trial Visit must be monitored and followed up by the Investigator until stabilization or until the outcome is known, unless the subject is documented as “lost to follow-up”. Reasonable attempts to obtain this information must be made and documented. It is also the responsibility of the Investigator to ensure that any necessary additional therapeutic measures and follow-up procedures are performed.

#### **7.4.2 Pregnancy and In Utero Drug Exposure**

Only pregnancies considered by the Investigator to be related to trial treatment (for example, resulting from a drug interaction with a contraceptive medication) are considered to be AEs. However, all pregnancies with an estimated conception date during the period defined in Section 7.4.1.3 must be recorded by convention in the AE page/section of the eCRF. The same rule applies to pregnancies in female subjects and to pregnancies in female partners of male subjects. The Investigator must notify the Sponsor/designee in an expedited manner of any pregnancy using the Pregnancy Report Form, which must be transmitted according to the same process as described for SAE reporting in Section 7.4.1.4.

Investigators must actively follow up, document and report on the outcome of all these pregnancies, even if the subjects are withdrawn from the trial.

The Investigator must notify the Sponsor/designee of these outcomes using the Pregnancy Report Form. If an abnormal outcome occurs, the SAE Report Form will be used if the subject sustains an event and the Parent-Child/Fetus Adverse Event Report Form if the child/fetus sustains an event.

Any abnormal outcome must be reported in an expedited manner as described in Section [7.4.1.4](#), while normal outcomes must be reported within 45 days after delivery.

In the event of a pregnancy in a subject occurring during the course of the trial, the subject must be discontinued from trial medication immediately. The Sponsor/designee must be notified without delay and the subject must be followed as mentioned above.

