**Table 2 Schedule of Assessments - Period 2 (Administration of Tepotinib and Dabigatran Etexilate)**

Assessment/ Activity	Study Period 2							End of Trial Visit a
	Day 1	Day 2 - 6	Day 7	Day 8	Day 9	Day 10	Day 11	
Hospitalization	X	X	X	X	X	X	X j	
Ambulatory Visits								X
Physical examination								X
Vital signs (blood pressure, pulse rate, body temperature)	X b	X b	X b	X c	X c	X c	X c	X
12-lead ECG	X d	X						
Clinical laboratory (hematology, biochemistry, urinalysis)	X e	X e	X e	X e			X e	X
Coagulation	X i			X i	X i			X
Serum pregnancy test								X
Administration of tepotinib	X f	X f	X f	X f				
Administration of dabigatran etexilate				X f				
PK blood sampling (tepotinib and its metabolites)		X g	X g	X g				
PK blood sampling total dabigatran (unconjugated and conjugated)				X h	X h	X h	X h	
Adverse events	←-----→							X
Concomitant medication	←-----→							X

ECG = electrocardiogram, PK = pharmacokinetics

**Adverse events and concomitant medication will be assessed from screening throughout the whole study until End of trial Visit.**

- a 7 ± 1 days after last drug administration in Period 2 (Day 15).
- b Vital signs (blood pressure and pulse rate) will be measured after at least 5 min rest before each (within 60 min prior to dosing) and 6 h after each tepotinib administration.
- c Vital signs will be measured after at least 5 min rest before (within 60 min prior to dosing) as well as 4, 8, 24, 48 and 72 h after the combined dabigatran etexilate and tepotinib administration.
- d After at least 5 min rest before each time point 12-lead ECGs will be recorded and printed out. Days 1 to 7 within 60 min prior to dosing and 6 h after each tepotinib administration. Day 8 within 60 min prior to dosing, as well as 4, 8, 24, 48 and 72 h after the combined dabigatran etexilate and tepotinib administration.
- e Laboratory assessments will be performed on Day 1, 2, 7 and 8 pre-dose, and on Day 11.

- f On Days 1 to 7, 500 mg tepotinib will be administered together with 240 mL of water 30 min after start of a standardized breakfast (completely consumed within 25 min).  

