## **5.2.2                    Scientific Rationale for Trial Design**

The study design and endpoints are typical for a drug interaction study of this type. The effect of tepotinib on P-gp by measurement of the PK of the P-gp substrate dabigatran etexilate will be investigated. Thus, dabigatran etexilate will be administered as a single dose once alone and once at steady state of tepotinib.

The study will utilize a single sequence crossover design with both treatments applied to the same subject. No carryover of dabigatran is expected between the first and second dose due to sufficient wash-out time. Moreover, the total dabigatran concentration should be below the quantification limit when starting the multiple dosing of tepotinib (period of 72 h, considering a mean elimination  $t_{1/2}$  [GeoMean] of about 8.4 h for dabigatran in healthy adult subjects [1]). It is anticipated that a possible period effect is very small and negligible compared to relevant treatment effects. The potential drug-drug interaction investigated in this study is expected to occur mainly in the intestine, where the P-gp mediated efflux of dabigatran etexilate could be inhibited by tepotinib. However, the effect on dabigatran will only be measured indirectly by the concentration-time profile of total dabigatran (unconjugated plus conjugated) in plasma.

Healthy subjects will be included in the study to minimize variability, which is expected to be higher in a patient population. Non-clinical safety investigations did not reveal a genotoxicity potential or other findings with relevance for human use. Therefore, it is reasonable that tepotinib can be administered to healthy subjects such as in this study in which careful safety monitoring is conducted. Knowing that tepotinib shows teratogenic effects, only healthy women that are postmenopausal or surgically sterile (ie, due to hysterectomy, or bilateral oophorectomy, or bilateral salpingectomy) will be enrolled in this study and male subjects must take precautions with female partners.

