### 5.3.1 Inclusion Criteria

To be eligible, the subject must fulfill all the following criteria:

1. Male or female, aged 18 to 44 years inclusive (at Screening)
2. Body mass index (BMI)  $\geq 18.5$  and  $\leq 29.9$  kg/m^2 and body weight between 50 to 100 kg, inclusive (at Screening)
3. A female participant is eligible to participate if she is of non-childbearing potential, confirmed at Screening, by fulfilling at least one of the following criteria:
  - Females who are postmenopausal (age-related amenorrhea  $\geq 12$  consecutive months and increased follicle-stimulating hormone [FSH]  $> 40$  mIU/mL)
  - Documentation of irreversible surgical sterilization by hysterectomy, or bilateral oophorectomy, or bilateral salpingectomy
4. A male participant must agree to use and to have his female partner of childbearing potential to use highly effective method of contraception (ie methods with a failure rate of less than 1% per year) as detailed in the Clinical Trial Facilitation Group (CTFG) recommendations [8] during the period of participation in the study and for at least 3 months after the last investigational medicinal product (IMP) administration (see Appendix III). Males must also refrain from donating sperm during this period and should always use a barrier method such as condom concomitantly. The male participants will be asked to report pregnancies in their female partners up to 3 months after the last IMP intake
5. Subject must be healthy, as assessed by the Investigator, with no clinically significant abnormality identified on physical examination and no active clinically significant disorder, condition, infection or disease that would pose a risk to subject safety or interfere with the study evaluation, procedures, or completion (at Screening and Day -1)
6. Subject must have given written informed consent before any study-related activities are carried out and must be able to understand the full nature and purpose of the study, including possible risks and adverse effects
7. All values for hematology, coagulation, and biochemistry tests of blood and urinalysis within the normal range (at Screening). Minor (solitary) non-clinically relevant deviation(s) are allowed as judged by the Investigator; however, amylase, lipase and alanine-amino-transferase [ALT] or aspartate-amino-transferase [AST] values should not exceed the upper limit of normal (ULN).

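### Are partner pregnancies conceived after the End of Trial Visit left without recording or follow-up?

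*Protocol*

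**What the plan says.** Five places bear on this point.

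- **Protocol 5.3.1, inclusion criterion 4.** Men and their partners use highly effective contraception during participation and for at least 3 months after the last dose. In addition, "The male participants will be asked to report pregnancies in their female partners up to 3 months after the last IMP intake".
- **Protocol 7.4.2.** On recording, "all pregnancies with an estimated conception date during the period defined in Section 7.4.1.3 must be recorded by convention in the AE page/section", and "The same rule applies to pregnancies in female subjects and to pregnancies in female partners of male subjects". The next sentence deals with notification: "The Investigator must notify the Sponsor/designee in an expedited manner of any pregnancy using the Pregnancy Report Form", sent by the route used for SAEs. A new paragraph then says: "Investigators must actively follow up, document and report on the outcome of all these pregnancies", even where the subject has been withdrawn. Outcomes go on the same form. Abnormal outcomes are expedited, and normal ones are due within 45 days of delivery.
- **Protocol 7.4.1.3.** The reporting period starts at informed consent "and continues until the End of Trial Visit". SAEs judged related to the IMPs are reportable at any later time.
- **Protocol Table 2, footnote a, and 7.1.3.** The End of Trial Visit falls 7 ± 1 days after the last dose, on Day 15 of Period 2.
- **SAP 15.1.1.** The adverse events analysed are those from informed consent to the End of Trial Visit.

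**The concern.** The request to the men and the instruction to the investigator run on different clocks. A man may report a partner pregnancy up to 3 months after his last dose, but the date limit in 7.4.2 shuts about a week after that dose. If the limit governed everything in 7.4.2, most of the reports that inclusion criterion 4 invites would arrive at a site with no instruction to record them, notify them or follow them to outcome.

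The subject matter makes that uncomfortable. Section 5.2.2 excludes women of childbearing potential on the ground stated as "Knowing that tepotinib shows teratogenic effects", so a partner pregnancy is the fetal exposure route the protocol still has to watch. No visit is scheduled after Day 15, so the site depends on the text. The provision for related SAEs is only partial cover, because it needs both an SAE and a judgement that it is related. The mismatch has a plain origin: Amendment 2 added the reporting sentence to inclusion criterion 4, and its list of changes shows none to 7.4.2.

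**Working it through.** **1. The two windows.** The last dose is on Day 8 of Period 2, and 8 + 7 = 15 reproduces the Day 15 of Table 2. With the ± 1 day, the conception window in 7.4.2 closes 6 to 8 days after the last dose. Taking 3 calendar months as 89 to 92 days (an assumption), the remainder is:

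- shortest: 89 − 8 = 81 days, or 81/89 = 91% of the 3 months
- longest: 92 − 6 = 86 days, or 86/92 = 93%

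**2. What those days measure.** Inclusion criterion 4 runs on the date the man reports, and 7.4.2 runs on the estimated date of conception. Subtracting one from the other treats both as conception dates, so 81 to 86 days is a maximum. A pregnancy conceived near the end of the third month would not be known in time to be reported within it. The documents give no time to recognition. If 2 to 5 weeks is assumed, the reportable part is 81 − 35 = 46 days to 86 − 14 = 72 days. A pregnancy conceived before the visit and reported later already falls inside the recording rule.

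**3. Duty by duty.**

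| Duty in 7.4.2 | Limit in the text | Partner conception after the visit |
|---|---|---|
| Entry on the AE page | Conception within the 7.4.1.3 period | Not required |
| Expedited notification on the Pregnancy Report Form | None | Required |
| Follow-up to outcome | Depends on what *these pregnancies* refers to | Required on the natural reading |
| Outcome reported on the same form | Follows the line above | Required on the natural reading |

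**4. The natural reading.** The sentence just before the follow-up duty is the notification sentence, which has no date limit. The date-limited recording sentence stands further back. The outcomes are then reported on the form that the notification sentence introduces. Position and form both tie follow-up to every notified pregnancy.

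**5. Expected cases.** Assume 20 men, each with a partner of childbearing potential, and a failure rate of 1% per year, the ceiling that criterion 4 sets for highly effective methods:

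- 20 × 0.01 × 81/365 = 0.044
- 20 × 0.01 × 86/365 = 0.047

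These figures do not count the additional barrier method. They are not a bound: note a in Appendix III warns that typical-use rates may differ, and Sections 5.5.1 and 5.5.2 allow subjects to be replaced. At an assumed 5% per year the larger figure becomes 20 × 0.05 × 86/365 = 0.24, still below one case.

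**6. Drug remaining.** Section 5.2.3 gives a half-life of about 30 h. If decline is mono-exponential, the fraction left 6 days after the last dose is 2^(−144/30) = 2^(−4.8) = 3.6%, and after 8 days it is 2^(−192/30) = 2^(−6.4) = 1.2%. This fits the statement in 5.2.2 that the visit covers elimination of tepotinib. Conceptions in the gap come after that point.

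**7. Effect on the analysis.** The primary endpoints are AUC and C_max of total dabigatran, which a partner's pregnancy does not touch. An AE-page entry for a later conception would lie outside the window in SAP 15.1.1, so it would enter no planned adverse event table.

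**The case for a change.** The strongest case for a change is that notification is not follow-up. An investigator could read *these pregnancies* as those in the date-limited sentence and stop after sending the form. The protocol asks men for these reports and calls the drug teratogenic, so an unambiguous instruction would be cheap: one or two sentences built on the 3-month period already in the document. Rarity is a weak defence in safety reporting, because the purpose is to handle the single case properly.

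Part of this stands. The follow-up sentence could be clearer, and the protocol does not say whether the 3 months in inclusion criterion 4 refers to conception or to reporting. The 3-month precaution also remains in force whatever the elimination arithmetic shows.

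The rest does not carry. The narrow reading passes over the sentence immediately before and the form shared by notification and outcome. Under the natural reading, a clarifying sentence would restate a duty that already exists. Tying the AE-page entry to the AE collection period is coherent, since the text describes that entry as a convention and the Pregnancy Report Form is the safety route. Extending the conception window in 7.4.2 to 3 months would not align the passages either. The request to the men would still end at 3 months, so conceptions late in that window would be covered by a rule the site has no planned way to learn about.

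**Conclusion.** The concern does not call for a change. Inclusion criterion 4 governs what men are asked to report. Section 7.4.2 governs what the investigator does with it. The two passages differ without contradicting each other. A site that follows 7.4.2 as written would notify the sponsor of a late partner conception and, on the natural reading, follow it to outcome. What is missing is an AE-page entry, which would feed no planned analysis.

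The gap affects at most 81 to 86 days of conception dates, and about 46 to 72 days if recognition takes 2 to 5 weeks. It carries roughly 0.05 expected pregnancies under consistent contraceptive use. Those figures rest on calendar months of 89 to 92 days, on 20 men all with fertile partners, and on a failure rate of 1% per year. The conclusion does not depend on them, because it rests on the undated notification duty and on the follow-up duty attached to it. This is a gap in wording that investigators and safety staff would fill sensibly, with no effect on the PK comparison, sample size, power or safety tables.
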